## 2. STUDY OBJECTIVES

### 2.1. Primary Objective

To evaluate the prophylactic efficacy of REGN1908-1909 (anti-Fel d 1) administered as a single dose on day 1 in cat-allergic asthmatic patients not living with a cat in the prevention of a Controlled Cat Allergen Challenge-induced early asthmatic response (EAR) assessed by measures of lung function (FEV1) compared to placebo-treated patients on day 8.

### 2.2. Secondary Objective(s)

#### Secondary Efficacy Objectives

- To evaluate the prophylactic efficacy of REGN1908-1909 administered as a single dose on day 1 in cat-allergic asthmatic patients not living with a cat, in the prevention of a Controlled Cat Allergen Challenge-induced:
  - Early asthmatic response (EAR) assessed by measures of lung function (FEV1) compared to placebo-treated patients on days 29, 57, and 85
  - Allergic rhinitis symptoms assessed by TNSS compared to placebo patients on days 8, 29, 57, and 85
  - Ocular symptoms assessed by total ocular symptom score (TOSS) compared to placebo patients on days 8, 29, 57, and 85
- To evaluate the prophylactic efficacy of REGN1908-1909 administered as a single dose on day 1 in cat-allergic asthmatic patients not living with a cat to increase the exposure to cat allergen, measured as a product of minute ventilation and time, required to induce EAR in a Controlled Cat Allergen Challenge ( $40 \text{ ng}/\text{m}^3$  Fel d 1 allergen  $\times$  minute ventilation  $\times$  time) as compared to placebo patients on days 8, 29, 57, and 85

**Secondary Safety Objective:** To evaluate the safety and tolerability of REGN1908-1909 vs. placebo in patients with cat allergen-triggered asthma.

## 2.3. Exploratory Objective(s)

### 2.3.1. Exploratory Efficacy Objectives

- To evaluate LAR on days 8, 29, 57, and 85
- To evaluate whether a single prophylactic SC administration of REGN1908-1909 inhibits a wheal-and-flare response to a skin prick test with serial allergen titration with cat allergen in patients with cat allergen-triggered asthma and AR with or without conjunctivitis on days 29 and 85
- To evaluate the prophylactic efficacy of REGN1908-1909 in cat-allergic patients not living with a cat to reduce respiratory symptoms induced by a Controlled Cat Allergen Challenge on days 8, 29, 57, and 85 as measured by chest symptom questions
- To assess the prophylactic effect of REGN1908-1909 on biochemical measures of asthma control (FeNO) in patients with cat allergen-triggered asthma induced by a Controlled Cat Allergen Challenge on days 30 and 86 and measured 24 hours after challenge
- To assess the prophylactic effect of REGN1908-1909 on TNSS, TOSS, and chest symptoms up to 24 hours after leaving the EEU
- To assess the prophylactic effect of REGN1908-1909 on objective measures of nasal congestion (PNIF) in patients with cat allergen-triggered asthma induced by a Cat Allergen Challenge on 8, 29, 57, and 85
- To assess the relationship between baseline cat allergen-specific IgE levels (cat hair sIgE, Fel d 1 sIgE), total IgE, and the ratio of cat allergen-specific IgE/total IgE (cat hair sIgE/total IgE and Fel d 1-specific IgE/total IgE levels) and efficacy of REGN1908-1909
- To assess the relationship between cat allergen-specific IgE levels (Fel d 2, Fel d 4, Fel d 7, and other common allergens) at screening and baseline to evaluate the relationship between response to REGN1908-1909 and poly/mono-sensitization
- To assess the extent of REGN1908-1909 interference with the measurement of endogenous anti-Fel d1 IgE in baseline samples and its relationship to clinical benefit
- To assess the degree to which REGN1908-1909 prevents induction of type 2 inflammation in the nasal mucosa as assessed by RNA sequencing of nasal brushing on day 29.

### **2.3.2. Exploratory Pharmacokinetic Objective**

To characterize the concentration-time profile of REGN1908 and REGN1909 after a single SC dose.

### **2.3.3. Exploratory Immunogenicity Objective**

To assess the incidence of treatment-emergent anti-drug antibodies (ADA) to REGN1908-1909 in patients with cat allergen-triggered asthma and AR with or without conjunctivitis over time.

## **3. HYPOTHESIS AND RATIONALE**

### **3.1. Hypothesis**

A single SC dose of REGN1908-1909 600 mg (anti-Fel d 1) will reduce cat allergen-induced bronchoconstriction, as measured by an increase in time to EAR upon Cat Allergen Challenge in an EEU, in cat-allergic asthmatic patients not living with a cat compared to placebo-treated patients.

### **3.2. Rationale**

#### **3.2.1. Rationale for Study Design**

An EEU that simulates natural exposure and provides standardized and reproducible cat allergen levels will be used to demonstrate the effectiveness of REGN1908-1909. Environmental exposure units have been used for modeling environmental exposure and response to a variety of anti-allergic agents, including antihistamines, anti-leukotrienes, intranasal and inhaled corticosteroids, and immunologics (Wood, 1995) (Perry, 2004) (Corren, 2011) (Patel, 2013). The EEU provides a means of simultaneously exposing upper and lower airways to uniform concentrations and particle sizes of allergen under uniform conditions, including CO2 levels, humidity, and temperature. The nebulized cat hair extract concentration that will be used in this study is 40 ng/m^3 Fel d 1. Forty (40) ng/m^3 Fel d 1 is the equivalent concentration that patients experience upon live cat exposure in homes where cats live (Blay, 1990) (Custovic, 1998) (Bollinger 1996) (Bollinger 1998). When tested in an EEU, 40 ng/m^3 (but not 20 ng/m^3) Fel d 1 produced a reduction in FEV1  $\geq 20\%$  in over 50% of cat-allergic GINA 1 asthmatic patients (Gherasim, 2018). In the current study, patients will be exposed to a placebo exposure of saline only in the EEU during screening to exclude patients who have a non-specific reduction in FEV1 upon EEU exposure. Patients who experience a non-specific reduction in FEV1  $> 10\%$  in 3 consecutive spirometry measurements will be excluded from the study (Diamant, 2014). Patients will next undergo a screening EEU exposure to nebulized cat hair extract (40 ng/m^3 Fel d 1). Patients who fail to experience a reduction in FEV1  $\geq 20\%$  within 2 hours in the Cat Allergen Challenge in the EEU will be excluded from the study. FEV1  $\geq 20\%$  is considered to be a clinically significant reduction and this threshold has been used for previous inhaled allergen bronchoprovocation tests (Diamant, 2014) (O'Byrne, 2009).

Patients who live with a cat will not be allowed to enter the study because these persons have a modified immune system with high levels of specific “blocking antibodies” IgG/IgG4 which may ameliorate the IgE-mediated allergic response (Erwin, 2014). Since this type of immune

response might induce clinical tolerance, diminishing the severity of symptoms upon allergen exposure, this study will exclude patients living with cats. Patients with moderate and severe asthma (GINA 2-5) will be excluded from the study, as moderate asthmatic patients are unable to tolerate challenges with cat allergen for longer than 30 minutes ([Corren, 2011](#)).

The follow-up period of 16 weeks (12 weeks of assessment plus 4-week safety follow-up) after the single dose of REGN1908-1909, plus an additional 30 days of follow-up for any SAE that occurs after study completion, represents a follow-up period of approximately 5 months, within the 4 to 5 half-life window for antibody levels to fall to largely undetectable levels. Serious adverse events considered by the investigator to be related to the investigational product are to be reported even if onset is greater than 30 days from the end of study.

### **3.2.2. Environmental Exposure Unit**

Alyatec's EEU is a 65 m^2 International Standards Organization 8 cleanroom (Standard 14644-1) with continuous air circulation, containing 20 seats to accommodate up to 20 patients at 1 time, and with an anteroom and exit room. The EEU contains 10 particle counters spread equally throughout the room, and glass fiber filters adjacent to seats to be used for Fel d 1 allergen testing by ELISA. Standardized, commercially available cat hair extract prepared by a pharmacist is nebulized into the EEU through a specialized system that maintains consistent particle counts and Fel d 1 counts approximating 40 ng/m^3 across the 20 seat positions of the EEU. Particle counts and Fel d 1 counts fall below the limit of detection within minutes of stopping the nebulization and Fel d 1 measurements are below the limit of quantification outside of the EEU (eg, in the observation area and in the rest rooms). Other allergens have been tested in the EEU, observation room, and the rest rooms and are below the limit of quantification (eg, house dust mite, birch), suggesting that there is no cross-contamination of allergens. During each exposure, the patients wear protective suits (TS Plus Microgard 2000) to ensure that no contaminant enters or exits the EEU. The cleaning procedure after each EEU exposure session includes the following: rinsing of the nebulization system, disinfectant of the floor, walls, the armchairs, and of all the small material stored in the EEU (Ecowipes, THX medical). Additionally, air qualification is performed by an independent company (Air Qualif) 4 times a year to test for the absence of bacteria and molds in the EEU.

### **3.2.3. Rationale for Dose Selection**

#### **Dose and Regimen of REGN1908-1909**

A single SC dose of 600 mg REGN1908-1909 is the highest dose previously tested in the first-in-human (FIH) study with cat-sensitized and allergic but otherwise healthy patients. This dose of REGN1908-1909 also appeared to be efficacious, reducing the TNSS in a nasal allergen challenge (NAC) study, a proof-of-mechanism (POM) study in cat-induced AR patients, R1908-1909-ALG-1325. This dose has been well tolerated and may provide effect for up to 12 weeks. The pharmacokinetic (PK) profiles of both REGN1908 and REGN1909 were characterized by linear and dose-proportional kinetics. The terminal half-lives of total REGN1908 and REGN1909 were determined to be approximately 30 ( $\pm 7$ ) and 21 ( $\pm 3$ ) days (Standard Deviation), respectively.

### 3.2.4. Rationale for Endpoints

Inhaled allergen bronchoprovocation tests have been used to study the pathophysiology of asthmatic responses to allergens (Popa, 2001) as well as to study the efficacy of anti-allergy therapeutic interventions. For example, Corren et al. reported that omalizumab, which inhibits the binding of IgE to the high-affinity IgE receptors on the surface of mast cells and basophils, reduced bronchoconstriction, as measured by a reduction in FEV1, in cat-allergic asthmatics in a live Cat Allergen Challenge (Corren, 2011).

To determine the efficacy of REGN1908-1909 to reduce bronchoconstriction in cat-allergic patients with asthma, an inhaled allergen bronchoprovocation test using a cat allergen EEU will be used. FEV1 will be measured by spirometry using portable hand-held devices at baseline and during the Cat Allergen Challenge in the EEU until the patient experiences an FEV1 reduction  $\geq 20\%$  of the baseline measurement or when the patient voluntarily departs the EEU due to clinically significant allergic and/or asthma symptoms. A reduction in FEV1  $\geq 20\%$  is considered to be clinically significant (Popa, 2001) and is achievable in patients with mild asthma (GINA 1). In the Alyatec validation study using the cat allergen EEU model to evaluate bronchoconstriction in GINA 1 mild asthmatics allergic to cat, the mean reduction in FEV1 during early and LAR was -28.1% range (-20.2 to -44.6) and -19.5% range (-14.9 to -23.5) respectively. Patients experienced EARs as early as within 30 minutes of exposure in the EEU to as late as 121 minutes, but the mean time to an EAR was 60 minutes (median of 58 minutes) and the mean time to a LAR was 180 minutes (Gherasim, 2018).

In the current study which will use the cat allergen EEU model, the primary endpoint is to assess the time to EAR during 4 hours of continuous exposure to 40 ng/m^3 of cat allergen in patients receiving 1 dose of REGN1908-1909 compared to placebo at day 8. Secondary endpoints are to assess the time to EAR in the cat allergen EEU at day 29 (week 4), day 57 (week 8), and day 85 (week 12) in patients receiving REGN1908-1909 compared to placebo.

Allergic rhinitis and conjunctivitis symptom scores and chest symptom questions will be measured at baseline, during the Cat Allergen Challenge, and for 24 hours following the challenge. Total nasal symptom score is based on regulatory (FDA and EMA) guidance for assessment of AR. Individual nasal symptoms, including rhinorrhea, nasal congestion, nasal itching, and sneezing are evaluated on a 4-point Likert scale (0, none; 1, mild; 2, moderate; and 3, severe) and combined to give the TNSS with a maximum score of 12. Individual ocular symptoms for itching/burning, redness, swelling/puffiness, and tearing/watery eyes are evaluated on a 4-point Likert scale (0, none; 1, mild; 2, moderate; and 3, severe) and combined to give the TOSS, with a maximum score of 12. Individual chest symptoms for chest tightness/shortness of breath/trouble breathing, wheezing, and coughing are evaluated on a 4-point Likert scale (0, none; 1, mild; 2, moderate; and 3, severe). In the omalizumab Cat Allergen Challenge study, there was a significantly lower decrease in the AUC of the change from pre-challenge values in the chest symptom questions (2.1 per hour vs. 5.6 per hour, p <.0001) and a combined nasal-ocular symptom score (NOSS) (2.5 per hour vs. 5.2 per hour, p <.0002 in patients treated with omalizumab as compared to placebo (Corren, 2011). In an allergen challenge in an EEU, allergic rhinoconjunctivitis symptoms typically peak at 3 hours (Ellis, 2017) (Horak, 2009), therefore patients who experience a reduction in FEV1  $\geq 20\%$  in less than 3 hours may not reach their peak allergy symptom scores. However, symptom scores (TNSS, TOSS, chest symptom questions) will be measured every 20 minutes during the cat allergen exposure in the EEU, every

hour for 6 hours following EAR, and thereafter every 2 hours, except when the patient is sleeping, for up to 18 hours after leaving the clinical unit, to compare patients receiving REGN1908-1909 to placebo.

The skin prick test with serial cat allergen titration assesses the early phase reaction (EPR) at 0-60 min. The early phase reaction is characterized by histamine release and is thought to reflect cutaneous mast cell degranulation upon allergen exposure. In the proof-of-mechanism (POM) study in cat-induced AR patients, R1908-1909-ALG-1325, the percent change from baseline in normalized average wheal diameter AUC of titrated (100-33,000 SQU/mL) cat hair extract skin prick test, read 15 min after administration on study days 29 and 85, was significantly reduced in REGN1908-1909-treated patients as compared to placebo-treated patients ([Orengo, 2018](#)). These data suggest that the skin prick test with serial cat allergen titration can be used to test pharmacodynamics of 1 dose of REGN1908-1909 in this study.

Serum antibodies against total cat hair and Fel d 1 will be measured to assess the levels of clinical sensitization against cat in patients prior to the beginning of treatment. As has been widely shown in SIT studies, clinical sensitization to a specific allergen is associated with decreased allergen-specific IgE over time. Concentrations of allergen-specific Ig subclasses, including IgA, IgG1, and IgG4, also increase concomitantly during clinical desensitization therapy. These protective antibodies are considered to be serum “IgE-blocking factors” ([Shamji, 2012](#)) and contribute to the induction of desensitization.

The sponsor hypothesizes that REGN1908-1909 may reduce the induction of genes and inflammatory pathways associated with type 2 inflammation post-EEU exposure. Existing data in the literature suggest that type 2 inflammation in asthmatic or AR patients could be detected by gene expression analysis of nasal tissue samples, collected either by nasal brushing or nasal curettes. For instance, RNA expression analysis of type 2-associated genes in nasal brushings from 50 asthmatic patients and 50 healthy controls have identified “Th2-high” and “Th2-low” patients differentiated by the expression of 70 genes associated with type 2 pathways, including IL-13, IL-5, and periostin. The analysis also revealed that Th2-high patients were more likely to have atopy, atopic asthma, higher blood eosinophil counts, and rhinitis, compared with Th2-low patients. Nasal IL-13 expression was 3.9-fold higher in asthmatic participants who experienced an asthma exacerbation in the past year ([Poole, 2014](#)). In a study of AR patients treated with prednisone or placebo, nasal challenge with Timothy grass was performed. Eight hours post-NAC, significant increases in eosinophil-related gene-expression were detected in the nasal sampling of placebo-treated patients compared to baseline, but not in prednisone-treated patients ([Leaker, 2017](#)). These data suggest that transcriptome analysis of nasal brushings could be used to assess underlying type 2-driven inflammation.

## 4. STUDY VARIABLES

### 4.1. Demographic and Baseline Characteristics

Baseline characteristics will include standard demography (eg, age, weight, height, etc), disease characteristics including medical history, and medication history for each patient.

### 4.2. Primary and Secondary Endpoints

The primary endpoint in the study is the time to EAR upon Controlled Cat Allergen Challenge in an EEU on day 8.

The secondary endpoints are:

- Time to EAR upon Controlled Cat Allergen Challenge in an EEU on days 29, 57, and 85
- AUC of the percent change (%/h) in FEV1 induced by a Controlled Cat Allergen Challenge over the exposure interval (%/h) from baseline to the Controlled Cat Allergen Challenge on days 8, 29, 57, and 85
- AUC of the percent change (%/h) in patient-assessed nasal symptoms induced by a Controlled Cat Allergen Challenge over the exposure interval (%/h) from baseline to the Controlled Cat Allergen Challenge on days 8, 29, 57, and 85
- AUC of the percent change (%/h) in patient-assessed ocular symptoms induced by a Controlled Cat Allergen Challenge over the exposure interval (%/h) from baseline to the Controlled Cat Allergen Challenge on days 8, 29, 57, and 85
- Change and percent change in cat allergen quantity as experienced by patients during exposure (measured by  $40 \text{ ng}/\text{m}^3 \times \text{minute ventilation} \times \text{time}$ ) on days 8, 29, 57, and 85
- Incidence rates of treatment-emergent adverse events (TEAEs) and serious TEAEs through end of study

### 4.3. Exploratory Efficacy Variable

- Time to LAR upon Controlled Cat Allergen Challenge after an EEU exposure on days 8, 29, 57, and 85
- AUC of the percent change (%/h) in patient-assessed chest symptom question responses
- Levels of FeNO (measured in parts per billion, which is equivalent to nanoliters per liter) 24 hours after Controlled Cat Allergen Challenge (days 30 and 86)
- Peak nasal inspiratory flow (measured in nasal patency, L/min) measured during the EEU exposure according to [Table 1](#)

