#### **8.2.2.3. Chest Symptoms Questions**

Individual respiratory symptoms of chest tightness/shortness of breath/trouble breathing, wheezing, and coughing are evaluated on a 4-point Likert scale ranging from 0 (none) to 3 (severe).

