1.2.2. Secondary Objectives

Secondary Efficacy Objectives

- To evaluate the prophylactic efficacy of REGN1908-1909 administered as a single dose on day 1 in cat-allergic asthmatic patients not living with a cat, in the prevention of a Controlled Cat Allergen Challenge-induced:
 - Early asthmatic response (EAR) assessed by measures of lung function (FEV1) compared to placebo-treated patients on days 29, 57, and 85
 - Allergic rhinitis symptoms assessed by TNSS compared to placebo patients on days 8, 29, 57, and 85
 - Ocular symptoms assessed by total ocular symptom score (TOSS) compared to placebo patients on days 8, 29, 57, and 85
- To evaluate the prophylactic efficacy of REGN1908-1909 to increase the exposure to cat allergen, measured as a product of minute ventilation and time, required to induce

EAR in a Controlled Cat Allergen Challenge (Fel d 1 allergen concentration (ng/ m³)x minute ventilation x time) as compared to placebo patients on days 8, 29, 57, and 85

Secondary Safety Objective: To evaluate the safety and tolerability of REGN1908-1909 vs. placebo in patients with cat allergen-triggered asthma.

1.2.3. Modifications from SAP Version 1

The following modifications have been made from Version 1 of the SAP as a result of blinded review of the data prior to the first-step analysis:

- Limited biomarker variables and analysis methods have been incorporated.
- The wording in the secondary endpoints for the AUC of TNSS and TOSS have been updated; however, the corresponding objectives will remain the same. In blinded review of baseline data, it was noted that some patients were asymptomatic at baseline. Therefore, the percent change as originally proposed in the SAP cannot be utilized and these endpoints will use a change from baseline metric.
- Analysis methods for exploratory efficacy endpoints have been added.
- The calculation of the cat allergen quantity as experienced by the patient will use the recorded levels of Fel d 1 in the EEU, rather than the target level of 40 ng/m³.
- The PK and ADA sections have been updated.
- Additional clarifications and details added throughout.

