5.6.3. Analysis of Other Efficacy Variables

The time to LAR at each of the Controlled Cat Allergen Challenges in an EEU will also be explored. After the allergen challenge (when the patient exits the EEU), the patient is observed

onsite for 6 hours and then for an additional 18 hours at home. If a patient does not experience an LAR within the 24-hour period, their time to LAR will be censored at 24 hours.

The time to LAR will be defined as the time to a $\geq 15\%$ reduction in FEV1 during the 6-hour onsite observation period (adjudicated by the blinded investigators). During the at-home monitoring period up to 24 hours after the patient exits the EEU, the time to LAR will be defined as the time to a $\geq 15\%$ reduction in FEV1 (confirmed by two spirometry efforts within 5 minutes) along with either rescue medication use (any medication at any dose) within 1 hour or the presence of chest symptoms within 1 hour of the drop in FEV1 (adjudicated by the blinded investigators). Chest symptoms are identified by a response of Mild, Moderate or Severe to the chest symptom questions involving chest tightness, wheezing, cough, throat tightness, and difficulty breathing. Multiple asthma exacerbations during the observation period or at-home monitoring period within the same patient may be adjudicated by the site to be an extended LAR (no more than one LAR within 24 hours of leaving the EEU may be adjudicated, e.g. a subject cannot have more than one LAR within 24 hours of leaving the EEU).

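### The exploratory chest-symptom variable is still a percent change, undefined at a zero reference, and the SAP neither repairs it nor plans another chest-score analysis

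*Protocol*

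**What the plan says.** Two exploratory objectives in Protocol 2.3.1 rest on chest symptoms. One asks whether the drug works "to reduce respiratory symptoms induced by a Controlled Cat Allergen Challenge on days 8, 29, 57, and 85 as measured by chest symptom questions". The other is "To assess the prophylactic effect of REGN1908-1909 on TNSS, TOSS, and chest symptoms up to 24 hours after leaving the EEU".

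The matching variable in Protocol 4.3 is "AUC of the percent change (%/h) in patient-assessed chest symptom question responses". The entry gives no reference value, time interval, challenge days or total score. Protocol 8.2.2.3 describes the items as "Individual respiratory symptoms of chest tightness/shortness of breath/trouble breathing, wheezing, and coughing", each scored from 0 for none to 3 for severe.

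The questions are asked before each challenge, about every 20 minutes during it, hourly for 6 hours afterwards, and then every 2 hours at home while awake (Protocol 8.1.1, footnote 6).

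SAP 1.2.3 reports that in blinded review "it was noted that some patients were asymptomatic at baseline". It concludes that percent change cannot be used and moves the TNSS and TOSS endpoints to change from baseline. Chest symptoms are not mentioned there. The same list of modifications says that methods for exploratory efficacy endpoints were added.

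In SAP 5.6.3 chest symptoms appear only in the at-home LAR rule. A confirmed FEV1 fall of at least 15% counts if rescue medication or a chest symptom falls within 1 hour of it. The symptoms named there are "chest tightness, wheezing, cough, throat tightness, and difficulty breathing".

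**The concern.** The only chest-symptom metric in either document fails for any patient whose reference is zero. The sponsor found this weakness in two sibling scores and corrected those two only. The SAP presents itself as comprehensive, yet it has no chest-score analysis to take the place of the protocol's metric.

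The chest questions are the patient-reported lower-airway measure taken during the challenges, in a trial about bronchoconstriction. With no prespecified score, interval or model, any treatment comparison reported later would be post hoc, and a reader could not tell whether the choice of metric came before sight of the results.

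The differing symptom lists are a separate matter. They bear on a variable the SAP does analyse, because a reported symptom can decide whether an FEV1 fall at home counts as a LAR.

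**Working it through.** The plan gives no sample size, power or alpha for chest symptoms, so there is no figure to reproduce. The check is the arithmetic of the metric, followed by a comparison of the two documents.

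**1. The metric at zero.** Percent change = 100 × (x − ref) / ref, and change = x − ref. For follow-up scores x = 0, 1, 3 and 6:

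| ref | percent change | change |
|---|---|---|
| 0 | undefined for all four | 0, 1, 3, 6 |
| 1 | −100, 0, 200, 500 | −1, 0, 2, 5 |
| 2 | −100, −50, 50, 200 | −2, −1, 1, 4 |

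Percent change is also unstable near zero: a follow-up score of 3 reads as 200% from a reference of 1 and 50% from a reference of 2.

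**2. Which reference.** Protocol 4.3 does not say, so two readings are open.
- Pre-challenge score. A zero is plausible because patients have GINA 1 asthma and a screening ACT below 20 is exclusionary (Protocol 6.2.2, criterion 30).
- AUC at the baseline challenge. SAP 4.5.2 and 5.6.2 use this for TNSS and TOSS, and 5.6.2 provides a subgroup with a non-zero baseline AUC. A zero then requires no chest symptom throughout that challenge. This is likely rarer, since inclusion criterion 2e requires a fall in FEV1 of at least 20% in it. A fall in FEV1 does not guarantee a reported symptom, so zeros remain possible.

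Analysing the items singly makes zeros at least as frequent as analysing their sum, because the sum is zero only when every item is zero.

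**3. How many patients.** Neither document gives the share with a zero reference. If the share is p, percent change is defined for 60 × (1 − p) of the 60 planned patients. For assumed p of 10%, 25%, 50%, 75% and 90%, that is 54, 45, 30, 15 and 6. The width of this range shows that the number cannot be settled from the documents. Change in AUC has no zero-denominator problem at any p; it needs only data from both challenges.

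**4. Whether the SAP supplies another analysis.**
- 4.5.3 lists time to LAR, time to any asthmatic response, FeNO and the titrated skin prick test.
- 5.6.3 analyses those and allows peak TNSS and TOSS. Chest symptoms appear only in the at-home LAR rule.
- 6.2 defines the AUC for FEV1, TNSS and TOSS.
- 10.1 has no chest-symptom row.

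**5. The symptom lists.** The protocol's first item combines chest tightness, shortness of breath and trouble breathing. The SAP's separate chest tightness and difficulty breathing therefore partly unbundle it. Throat tightness is the one new symptom.

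**The case against.** The strongest reply is that no chest percent change is planned in the SAP, so nobody would be dropped for a zero denominator. The SAP also overrode the protocol's percent change for TNSS and TOSS without a protocol edit: Protocol 4.2 still carries it. What remains is an omitted exploratory variable. PNIF, also listed in Protocol 4.3, is missing from the SAP analyses too, which may indicate a deliberate narrowing. The Protocol Introduction mentions a separate exploratory biomarker report and then lists chest symptoms among the exploratory objectives.

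Most of this stands as a limit on the point, but it does not remove the gap. No document says that the chest objectives were dropped or deferred. For nasal brushing and the interference assay, Protocol 4.6 does say that results stay out of the clinical study report. Whether the biomarker report would cover chest symptoms is unclear.

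It is also fair that evidence of asymptomatic patients comes from TNSS and TOSS. Carrying it over to chest symptoms is an inference.

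Four stronger readings are tempting, and the documents do not support them:
- A reader might infer that half or more of the patients would be lost. That needs an assumed share of zeros, and it fits the pre-challenge reading better than the baseline-challenge reading used for TNSS and TOSS.
- A reader might infer that those lost would be the best-controlled patients. Nothing links a zero chest score to better control among patients who all had to meet the same ACT criterion.
- A reader might take the chest questions to be the only patient-reported lower-airway outcome. The ACT is also patient-reported, though it is used at screening and end of study as a safety measure.
- A reader might conclude that the objectives cannot be answered. The data are collected; what is missing is a planned analysis.

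**Conclusion.** The point holds as a gap in an exploratory analysis. Protocol 4.3 retains a metric that fails by the sponsor's own reasoning, and the SAP provides no replacement, so the chest-symptom part of two objectives in Protocol 2.3.1 has no usable planned analysis. This does not depend on which reference was intended or on how many patients have a zero. The omission is a matter of text, and at a zero reference the metric is undefined on either reading.

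The size in patients is unknown. The consequence is minor: the objectives are exploratory, carry no power claim and lie outside multiplicity control (Protocol 10.4.3.3). No primary or secondary conclusion changes. The mismatch in symptom lists is a smaller, separate point. It may disappear once the questionnaire and CRF, which are not part of these documents, are consulted.

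**What to change.** Add to SAP 4.5.3, 5.6.3 and 6.2 the change in AUC of the chest-symptom score from the baseline challenge to Days 8, 29, 57 and 85, using the TNSS algorithm and MMRM, with results labelled nominal. The entry should also:
- define the score, either item by item or as a stated sum of the items collected. The protocol defines no total, so a sum is a choice to be declared;
- use the symptom recording times. At about 20-minute spacing, 0 to 2 hours has six intervals (120 / 20), whereas the grid shown in SAP 6.2 has twelve;
- state how chest symptoms up to 24 hours after leaving the EEU will be summarised;
- note that this replaces the percent change in Protocol 4.3.

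Protocol 3.2.4 offers a precedent: it describes the omalizumab cat-challenge study's chest-symptom result as an AUC of change from pre-challenge values, not of percent change. If the sponsor does not want the analysis, the SAP should say that the objectives will be handled descriptively or dropped. Either decision should be recorded before unblinding.

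Separately, reconcile the symptom list in the at-home LAR rule in SAP 5.6.3 with Protocol 8.2.2.3 and the CRF.

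The cost is a short SAP revision, some programming adapted from TNSS, and one more exploratory result to interpret with caution. No new data are required.
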